- a) At the end of the 12 weeks, the interventional arm will reach a clinically meaningful change in walking ability, as compared to controls, measured by a change in the 6-MWT at twelve-week, and 12 months; the minimal clinically important difference (MCID) is defined as +12m (7).

- b) At the end of the 12 weeks, $\geq 15\%$ interventional treatment arm participants will give up smoking or have significantly reduced their daily smoking compared to less than $\leq 10\%$ in the control arm.
- c) At the end of the 12 weeks, $\geq 50\%$ of interventional treatment arm participants will improve their medication adherence from pre- until post-intervention as compared to $< 30\%$ in the control arm.
- d) Healthcare cost will be reduced at 12 month follow-up in the intervention arm.

III. METHODOLOGY

We will implement a randomized controlled study of a 12-week lifestyle intervention for patients with peripheral arterial disease, delivered via the digital platform Sidekick Health. Participants will be recruited and randomized in a 1:1 manner to the digitally delivered intervention + standard of care or standard of care only. The standard of care group will receive an information leaflet on important lifestyle factors for PAD and smoking cessation and medical adherence will be encouraged by the health care provider. The interventional arm will receive a digital program delivered to their mobile phone alongside standard of care. Replicating a real-life scenario a personalized approach will be applied in the interventional arm, especially regarding smokers. Therefore, two pathways are possible in the interventional arm in this trial, one for smokers who want assistance in smoking cessation (PAD-SC) and another for non-smokers or those who smoke and do not desire to quit (PAD-Reg). Patients will be followed up at 12 weeks. We aim to do a separate follow-up at twelve months. The primary outcome will be a change in pain-free and maximal walking ability, measured by the 6-minute walking test. Secondary outcomes will include smoking status change (in PAD-SC group as compared to the control arm), medication adherence and lifestyle changes (increased physical activity, changes in self-assessed stress/energy/sleep quality levels), health-related quality of life, and a reduced need for hospitalization or revascularization due to PAD at 12 months of follow up.

Subject selection

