Vascular Quality of Life Questionnaire (VascuQoL-6)	Yes	Yes	Yes
Morisky Medication Adherence Scale (MMAS-8)	Yes	Yes	Yes
Quality of life questionnaire – assessed by EQ5D5L	Yes	Yes	Yes
Assessment of health literacy (HLS-EU-Q16 Swedish version)	Yes	-	-
Carbon Monoxide breath monitor (smokers only)	Yes	Yes	Yes
Smoking Readiness to Quit Ladder (smokers only)	Yes	Yes	Yes
Daily frequency of cigarettes smoked (smokers only)	Yes	Yes	Yes
Intervention arm only			
In-app 6-minute walking test	Yes	Yes	Yes
Free-living physical activity (measured as total step count per day)	Yes (week 1)	Yes	-
In-app metrics (e.g. stress/sleep/energy level self-assessment)	Yes (week 1)	Yes	-

Measures – copies of questionnaires will be included in this protocol when finalized in section VIII below (Study Questionnaires)

IV. BIOSTATISTICAL ANALYSIS

Variables to be collected

Participants' demographic and background information, including age, gender, height, weight (and BMI), tobacco use, co-morbid medical or psychiatric conditions, and information on any current medical therapy they may or may not be receiving will be collected. All participants should be on the best medical PAD treatment available for them, and the control arm will receive an information leaflet about relevant lifestyle modifications for PAD. A 6MWT, questionnaires, and validated survey instruments (10) will be administered both pre-and post-intervention and 12 months from the start of the intervention.

Primary Outcomes (Intervention KPIs)

As far as possible, evaluation of endpoints will be done by evaluators blinded to the treatment assignment (PROBE design).

- Walking Ability: Change in patients objectively measured walking ability (measured by the 6-Minute Walk Distance Test) from pre- to post-intervention and 12 months.

Secondary Outcomes

- Smoking status: Change in patients' daily smoking patterns from pre to post-intervention and at twelve months. This will be based on information from the patient, supported by read-outs from the carbon monoxide breath monitor at baseline, 12 weeks and one year.
- Medication adherence improvement.
- Lifestyle behavioral changes (measured in-app):
 - Changes in free living physical activity, measured as total step count per day (from baseline to week 12)
 - Changes in self assessed stress levels, measured on an ordinal scale from 0-10 (from baseline to week 12)
 - Changes in self assessed energy levels, measured on an ordinal scale from 0-10 (from baseline to week 12)

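### The smoking endpoint has no single working definition, so whether hypothesis (b) is met can depend on how patients who cut down are classified

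*Combined protocol and SAP*

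**What the plan says.** The smoking endpoint is described in three places.

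- **Section II, hypothesis (b).** At 12 weeks, at least 15% of intervention participants "will give up smoking or have significantly reduced their daily smoking compared to less than" or equal to 10% of the control arm. This is a responder proportion with numerical targets. No size of reduction is given.
- **Section III.** "Secondary outcomes will include smoking status change (in PAD-SC group as compared to the control arm"). There is no rule for what counts as a change.
- **Section IV, Secondary Outcomes.** "Smoking status: Change in patients' daily smoking patterns from pre to post-intervention and at twelve months". The same item adds: "This will be based on information from the patient, supported by read-outs from the carbon monoxide breath monitor". It gives no carbon monoxide cut-off and no rule for a patient whose report and read-out disagree.

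Table 2 collects daily cigarette frequency and carbon monoxide in smokers at baseline, week 12 and 12 months. Statistical Methods compares changes in each outcome by t-tests or non-parametric tests, as appropriate. It reserves ANCOVA and mixed ANOVA for the primary outcome and names no method for a binary smoking event.

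**The concern.** A patient who cuts down but still smokes may be a responder under hypothesis (b), if the reduction is judged large enough. The same patient's place under Section III is unstated. Under Section IV the patient contributes some amount of change in a pattern, on a scale that is not specified. The 15% and 10% targets can apply only to a proportion of responders, and the one rule that yields a proportion depends on an undefined word. Statistical significance is a property of a comparison between groups and cannot classify one person's cigarette count.

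At stake is the verdict on a hypothesis with explicit numerical targets. Patients know their allocation, blinded evaluation is promised only as far as possible, and the outcome rests on what patients report. If the rule is not fixed in advance, it could be chosen with the results in view.

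**Working it through.** **1. The plan's own figures.** The plan has no calculation for the smoking endpoint. Its only sample size reproduces as a two-group, two-time-point interaction with f = 0.15, r = 0.25 and N = 134:

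λ = f² × N × m / (1 − r) = 0.0225 × 134 × 2 / 0.75 = 8.04, with 1 and 132 degrees of freedom, which gives power 0.804.

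That matches the stated 0.80 but uses no smoking rate, so it does not help to define the smoking event.

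**2. The three places side by side.**

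| Feature | Hypothesis (b) | Section III | Section IV |
|---|---|---|---|
| Quantity | Share who quit or significantly reduced | Change of status, undefined | Change in daily pattern, scale not stated |
| Time | Week 12 | Not tied to a visit in the outcome list | Week 12 and 12 months |
| Comparison | Intervention arm v control arm | PAD-SC group v control arm | Not stated |
| Does a patient who cuts down count? | Only if the reduction is significant, undefined | Not stated | Registers as change; no event rule |

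Table 2, Statistical Methods and Section VIII do not reconcile these.

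**3. Illustration.** All counts are assumptions, because the plan gives neither a quit rate nor a reduction rate. Take 25 baseline smokers per arm. Controls: 1 quits, 1 cuts down. Intervention: 2 quit, 3 cut down.

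- Composite: (2 + 3)/25 = 20% v (1 + 1)/25 = 8%. Both targets met; difference 12 points.
- Quitting only: 2/25 = 8% v 1/25 = 4%. The 15% target is missed; difference 4 points.

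The range between these depends on how many of the three intervention patients who cut down pass the threshold:

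| Counted as reduced | Intervention rate | At least 15%? |
|---|---|---|
| 0 | 2/25 = 8% | No |
| 1 | 3/25 = 12% | No |
| 2 | 4/25 = 16% | Yes |
| 3 | 5/25 = 20% | Yes |

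The control rate is 4% or 8%, within 10% either way. The result turns on whether at least two of three patients are counted, and the plan has no rule for that.

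**4. Denominator.** Hypothesis (b) speaks of arm participants, while the illustration uses smokers. With 67 per arm, the same patients give 5/67 = 7.5% v 2/67 = 3.0% by the composite, and the 15% target is missed under either rule. A 20% rate among smokers reaches 15% of the whole arm only if smokers are at least 15/20 = 75% of it. The denominator therefore has to be stated too.

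**The case against.** The strongest case on the other side is that the three texts can be read together. Section IV uses the label that Section III uses and explains it as change in daily smoking patterns. On that reading Sections III and IV are one measure that registers reduction, and hypothesis (b) is its responder form. The background and aim, which speak of reducing smoking, agree with this.

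This is fair, and it rules out a stronger claim that a reader might infer: that a patient who cuts down is an event under one section and expressly a non-event under another. Only hypothesis (b) states an event, and no section excludes such a patient. The exclusion follows only if status means smoker versus non-smoker. Some usage suggests that meaning. Randomisation is stratified by smoking status, and the readiness ladder separates cutting back from having quit. But the plan never says so.

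The harmonising reading still leaves the gap. A change in pattern is not a proportion, so the targets need a threshold that no section supplies.

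Two further inferences are unsupported. The documents give no rates showing that cutting down is more common than quitting. Nor do they support treating 15% and 10% as quit rates, since the figures are attached to the composite.

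It is also true that this is a secondary endpoint and the trial was not sized for it. For 15% v 10% with 67 per arm, two-sided 0.05, power = Φ[(0.05 − 1.96 × √(2 × 0.125 × 0.875/67)) / √((0.15 × 0.85 + 0.10 × 0.90)/67)] = Φ(−1.09), about 14%. If smokers are 30–50% of each arm (assumed), that is about 20–34 per arm and power is about 7–9%. This limits the weight of the point. It also means that hypothesis (b) is more likely to be judged by whether observed rates reach the targets than by a test, and that judgement is sensitive to a few classifications.

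**Conclusion.** The concern holds as a missing operational definition, not as a set of contradictory event rules. Hypothesis (b) carries numerical targets, but its event cannot be counted without a decision that the plan does not make. In the illustration that decision moves the intervention rate between 8% and 20% and the arm difference between 4 and 12 points, and so decides whether the 15% target is met.

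Those figures rest on assumed counts and a denominator of baseline smokers. They show that the result can turn, not how likely it is to turn. The primary walking outcome is unaffected. The change is still worth making because it is cheap and must be made before outcome data are seen to have any value.

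**What to change.** Use one definition in Section II, Section III and Section IV:

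- **Population and comparison.** Baseline smokers, compared by randomised arm. Smoking status is already a stratification factor, so this keeps the randomised comparison. The PAD-SC group in Section III is formed after randomisation by smokers who want help to quit, so comparing it with the whole control arm is not a randomised contrast.
- **Quitting.** Smoker at baseline and not smoking at the visit, at 12 weeks and 12 months. State how the carbon monoxide read-out is used and what happens when it disagrees with the patient's report.
- **Reduction.** Report it separately at the same visits, as the between-arm difference in cigarettes per day adjusted for the baseline count, with quitters entered as zero. This replaces an unadjusted t-test on change and needs no threshold.
- **Targets.** If the composite and its 15% and 10% figures are kept, fix a numerical reduction threshold before outcome data are seen. Otherwise state which measure the figures refer to and justify them.

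The cost is protocol and analysis-plan wording. Cigarette counts and carbon monoxide are already scheduled at all three visits. The drawback is that fewer patients may count as successes under hypothesis (b).

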Individuals willing to participate and who provide written informed consent to the study will be further assessed and screened based on the inclusion and exclusion criteria presented in Table 1.

Table 1. Participant Criteria

Inclusion	Exclusion
Adults with confirmed PAD referred to a vascular surgery unit for evaluation and treatment, currently on best medical treatment and own/have access to a mobile smartphone	Critical limb ischemia, prior amputation, or other diseases/impairment that limit the walking ability and the 6-minute walk test's proper conduct
Stable PAD disease and limb symptoms during the last 3 months.	Cognitive impairment
PAD is the activity-limiting disease	Prior revascularization less than one year ago
Abnormal resting ankle-brachial index (≤ 0.90), falsely elevated above 1.3 or a 30% post-exercise ABI reduction.	A planned revascularization procedure during the upcoming 12 months (known at baseline)

Subject enrollment

Patients will be recruited by a clinic nurse or a medical doctor at participating centers (via telephone or during a scheduled in-person visit). Once agreed to participate and after signing informed consent, then the inclusion and exclusion criteria will be explored. Patients failing the screening process (do not meet the inclusion/exclusion criteria) may not participate in this study. Reasons for screen failure will be documented, but no other data will be collected. Participants who meet the criteria will be randomized to intervention or usual care in a 1:1 manner.

Based on a G*power analysis, the total number of patients in the two groups (intervention and control) will be 134, 67 in the intervention group and 67 in the control group, with an anticipated effect size of $f = 0.15$, $\alpha = 0.05$, power = 0.80 and correlations between time points (baseline and final timepoint) estimated at $r=0.25$. Foreseeing an attrition rate of 15%, we aim to recruit 155 patients to the trial.

Study procedures

All participants:

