Analyses will be performed according to the intention-to-treat principle and per-protocol analyses. Baseline characteristics and raw score questionnaire outcomes will be summarized as mean and SD for continuous measures and absolute numbers and percentages in each group. Changes in each outcome between baseline, post-intervention, and later a 12-month follow-up will be compared between and within the groups using t-tests or non-parametric statistical tests as appropriate. For the between-group differences, 95% Confidence Intervals will be reported. Correlations will be run to explore relationships between variables. For the primary outcome analyses, Ancovas or Mixed Anovas (repeated measures anovas) will be used, correcting for covariates that are significantly different between groups. The size of the change in HRQoL will be related to minimal important change values for the VascuQoL-6. It will be further assessed through effect size calculations (effect size=the difference in mean values between baseline and follow-up, divided by the SD at baseline). Cohen's criteria for interpreting effect sizes will be applied (small, 0.2–0.5; moderate, 0.5–0.8 and large, over 0.8). The a priori level for statistical significance will be set at a 2-sided $P < .05$.

V. RISKS AND DISCOMFORTS

We expect minimal to no risks and discomforts to be associated with this study. The lifestyle/behavioral change program is guideline-compliant for PAD patients and has

been reviewed by several medical doctors, behavioral scientists, and specialists in vascular surgery. Psychosocial risks will be minimal as well.

VI. POTENTIAL BENEFITS

Potential Benefits to Participating Individuals

The hope is that the intervention will increase participants' walking ability, reducing IC symptoms and prevent revascularization, empower participants to change their lifestyle and smoking patterns for the better, or that they will quit smoking altogether. Further, this intervention may also improve other patient-reported outcomes (e.g., reduce stress, improve sleep) without causing significant harm. Although the expected benefits are limited for patients that are allocated to usual care in the study, the enhanced follow-up at 12 weeks and 12 months may allow for a more careful evaluation and subsequent treatment of their condition following the end of study.

Potential Benefits to Society

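### Hypothesis (c) judges medication adherence by an undefined percentage of patients who improve and is tied to no analysis; a baseline-adjusted comparison of the MMAS-8 score should be named instead

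*Combined protocol and SAP*

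**What the plan says.** - **Section II, Hypotheses, item (c).** The criterion is a percentage in each arm: at least 50% "of interventional treatment arm participants will improve their medication adherence from pre- until post-intervention as compared to" under 30% of controls. The item does not name an instrument or say what counts as improving.
- **Section III, Table 2, and the questionnaire pages.** The MMAS-8 is the only adherence instrument. It has seven yes/no items and one five-level item, and is taken in both arms at baseline, after week 12 and at 12 months. The questionnaire pages explain how the VascuQoL-6 total is formed, but give no such rule for the MMAS-8.
- **Section IV, Secondary Outcomes.** The outcome is listed only as "Medication adherence improvement", with no metric.
- **Section IV, Statistical Methods.** Changes in each outcome "will be compared between and within the groups using t-tests or non-parametric statistical tests as appropriate", with 95% confidence intervals for between-group differences. ANCOVA or mixed ANOVA is named for the primary outcome only. Significance is two-sided at 0.05.
- **Section III, Subject enrollment.** The number of patients "will be 134, 67 in the intervention group and 67 in the control group". Recruitment is set at 155 to allow for 15% attrition. Nothing in this calculation refers to adherence.

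**The concern.** Medication adherence is one of the four effects named in the specific aim. The only numerical criterion for it is the proportion improving, and that has two weaknesses.

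First, it discards information. A small gain and a large gain count the same, as do a patient who is stable and one who deteriorates. Take an artificial case on a worse/same/better scale scored −1, 0, +1. Controls have 10% worse and 30% better; the intervention arm has 40% worse and 50% better. Mean change is 0.30 − 0.10 = +0.20 in controls and 0.50 − 0.40 = +0.10 with the intervention. The average favours control, yet the proportion improving favours the intervention by 20 points.

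Second, it is loose. Improvement has no threshold, whereas the plan cites a minimal important difference for the walk test and minimal important change values for the VascuQoL-6. With hypothesis (c) worded as a percentage and the Statistical Methods worded as tests of change, one adherence claim could be settled by a comparison of proportions, a t-test or a rank test. The choice could be made after the data are seen.

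**Working it through.** **1. The plan's own figure.** The stated total is 134, with f = 0.15, α = 0.05, power 0.80 and correlation 0.25. For a repeated-measures ANOVA interaction (2 groups, 2 times), λ = f² × N × m / (1 − r) = 0.0225 × 134 × 2 / 0.75 = 8.04. With 1 and 132 degrees of freedom, power is 0.804. The figure reproduces. It does not come from hypothesis (c).

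**2. Power of the yes/no comparison.** Inputs: 0.50 v 0.30 (hypothesis c), 67 per arm (Subject enrollment), two-sided 0.05 (Statistical Methods).
- Null SE = √(2 × 0.40 × 0.60 / 67) = 0.0846.
- Alternative SE = √((0.25 + 0.21) / 67) = 0.0829.
- z = (0.20 − 1.96 × 0.0846) / 0.0829 = 0.41, so power is about 66%.
- Exact enumeration gives 65.4% for the uncorrected chi-square test and 59.0% for Fisher's test.
- 80% power would need 93 per arm.

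After planned attrition: 155 × 0.85 / 2 = 65.9 per arm, power about 65%. The 15% must not be taken off the 67 again, because recruiting 155 already allows for it.

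**3. Full score, whole distribution shifted.** The documents give no MMAS-8 mean, SD or expected change, so these are assumptions matched to 30% v 50% improving, at 67 per arm.
- Normal change score cut at zero: the implied difference is z(0.50) − z(0.30) = 0.524 SD. The noncentrality is 0.524 × √(67/2) = 3.03, and t-test power is 85%.
- Normal shift on a coarse five-level change score: 72% to 82% by simulation.
- Proportional odds on worse/same/better, odds ratio (0.50/0.50) / (0.30/0.70) = 2.33, with 10% to 40% of controls worsening: rank-test power 69% to 75% by simulation.

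**4. Full score, extra improvers drawn only from unchanged patients.** The rates are again 30% v 50%, but equal shares worsen in both arms. With 10% worsening, controls are 10/60/30 and intervention 10/40/50 (worse/same/better).
- Probability that an intervention patient does better than a control, counting ties as half: (0.50 × 0.70 + 0.40 × 0.10) + ½ × (0.01 + 0.24 + 0.15) = 0.59.
- Pooled shares are 0.10, 0.50 and 0.40, so the tie factor is 1 − (0.001 + 0.125 + 0.064) = 0.81.
- Null SE = √(135 × 0.81 / (12 × 67²)) = 0.045, z = 0.09 / 0.045 = 2.0, and power is just over 50%.

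Simulation gives 52%, 40% and 31% with 10%, 20% and 30% worsening. Other patterns of this kind, on five- or seven-level change scores, gave 15% to 62%. All lie below the yes/no test's roughly 65%.

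**5. Baseline adjustment.** With unit variance and correlation r, a change score has variance 2(1 − r) and ANCOVA has residual variance 1 − r². At r = 0.25 these are 1.50 and 0.94. The 0.25 is borrowed from the sample-size calculation and is only illustrative for the MMAS-8. The ratio 0.94/1.50 = 0.63 shows what adjustment can gain over an unadjusted test of change.

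**The case against.** The best defence is that the plan never commits to a test of proportions. The Statistical Methods promise tests of change in each outcome, adherence is a listed outcome, and the MMAS-8 is its instrument. A between-arm comparison of score change is therefore a natural reading, and the 66% is the power of a test that nobody has specified. This stands as far as it goes: a reader might infer that the plan will dichotomise the MMAS-8, and the documents do not settle that. It does not close the gap. Nothing links the change tests to hypothesis (c), the secondary outcome has no metric, and the stated criterion is still a percentage.

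A reader might also infer that the full score is always more powerful. It is not, as step 4 shows. An app that prompts some stable patients and does nothing for those who deteriorate could produce that pattern.

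Finally, hypothesis (c) is secondary, and the sample size was not built on it. It would be wrong to say that 66% contradicts the plan's 80%.

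**Conclusion.** The point holds as a gap in specification, with a better analysis available at little cost. Hypothesis (c) rests on an undefined and unjustified percentage and is not tied to any analysis. If it were tested as worded, power would be about 66% at 67 per arm, on the plan's own rates.

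The alternative has about 70% to 85% power if the intervention moves the whole distribution. It can have less than the yes/no test if the effect is confined to patients who would otherwise be unchanged. The documents contain nothing that decides between these patterns, so a power gain is likely under a general shift but not assured. In both patterns the full-score figures are for unadjusted tests; the gain from adjustment is shown only through the variance ratio in step 5.

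Two parts of the case depend on no power assumption. The percentage cannot distinguish stability from deterioration, and leaving the analysis open allows it to be chosen after the results are known.

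**What to change.** - **Hypothesis (c):** state that it is tested by a between-arm comparison of the week-12 MMAS-8 score using ANCOVA, adjusted for baseline MMAS-8 and the randomisation strata (site and smoking status), with the difference and its 95% confidence interval. Name a proportional-odds model with the same covariates, reported as an odds ratio with 95% confidence interval, if the score is strongly skewed or at its ceiling. Fix the rule for switching before the outcome data are seen.
- **Secondary Outcomes:** reword the adherence entry as the MMAS-8 score at week 12 relative to baseline, and state how the eight items form the total and which direction is better.
- **Statistical Methods:** link this analysis to hypothesis (c) explicitly.
- **Percentage improved:** keep it by arm as a descriptive summary, with improvement defined.

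The cost is wording in three places, with no new data, visits or patients. The downside is that a score difference or odds ratio is harder to read than a percentage, which is why the percentage stays in the report.
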